#### 4.3.1.2. Participant Exclusion Criteria

All participants meeting any of the exclusion criteria at baseline will be excluded from study participation.

1. Positive pregnancy test at screening or prior to infusion.
2. Female participant who is lactating.
3. Presence of significant psychiatric condition, that in the opinion of the site PI or appropriate sub-investigator, precludes study participation.
4. History of drug abuse or alcohol abuse within 6 months of enrollment that, in the opinion of the site PI or appropriate sub-investigator, precludes study participation.
5. Has a significant acute illness (with or without fever), as determined by the site PI or appropriate sub-investigator, within 72 hours prior to infusion.

If the participant meets all other eligibility criteria, they may be enrolled and dosed once they meet this eligibility criterion. If the illness resolves within the 28-day screening window, they do not need to be rescreened, otherwise they will need to be rescreened.

6. Currently enrolled in or plans to participate in another clinical trial with an investigational agent that will be received during the study-reporting period.
7. Has a history of significant hypersensitivity, intolerance, or allergy to any drug compound, vaccine, food, or other substance, unless approved by the Investigator (or designee).

*Sensitivity to glycine, citric acid, trisodium citrate, sorbitol, or polysorbate 80 (components of the study product) is exclusionary.*

8. Any history of an infusion reaction to any biologic product.
9. Receipt of a monoclonal antibody in the 180 days prior to infusion.
10. Receipt of a blood product within 120 days prior to infusion.
11. Received any live-attenuated vaccine in the 28 days prior or any other vaccine in the 14 days prior to infusion.
12. Has used any prohibited medication within 30 days prior to Day 1 or plans to use prohibited medication during the study.
13. Has clinically significant findings on 12-lead electrocardiogram.

*Clinical significance will be determined by a cardiologist. Examples of findings that will lead to exclusion are significant left ventricular hypertrophy, right or left bundle branch block, advanced A-V heart block, non-sinus rhythm (excluding isolated premature atrial contractions), pathologic Q wave abnormalities, significant ST-T wave changes, and prolonged QTc interval. Long QT interval is defined in males as a median QTcB greater than 450 msec or in females as a median QTcB greater than 460 msec (Bazett's correction) at screening.*

14. Abnormal vital signs (Grade 1 or higher) at screening or on Day 1.

*Grade 1 or higher is equivalent to:*

*Systolic blood pressure (SBP) > 140 mmHg or < 85 mmHg*

*Diastolic blood pressure (DBP) > 90 mmHg*

*Oral temperature  $\geq 38.0^{\circ}\text{C}$  ( $100.4^{\circ}\text{F}$ )*

15. Abnormal laboratory results that are Grade 1 or worse at screening based on the Toxicity Tables.

*Creatinine, alanine transaminase (ALT), hemoglobin (Hgb), platelets (PLT), white blood cell count (WBC), and total bilirubin (T bili).*

*Laboratory studies can be repeated once if an alternative, transient etiology for abnormal laboratory values is identified.*

16. Known, current human immunodeficiency virus (HIV), hepatitis B Virus (HBV), or hepatitis C virus (HCV) infection.

17. Has any medical disease or condition that, in the opinion of the site PI or appropriate sub-investigator, precludes study participation.

*Medical conditions include, but are not limited to, kidney disease with creatinine clearance  $< 90 \text{ mL/min}/1.73 \text{ cm}^2$  (CKD-EPI method); known active liver disease including steatosis; ischemic heart disease, clinically significant cardiac conduction disorder, arrhythmia requiring treatment, congenital long QT syndrome, uncompensated heart failure; diabetes requiring insulin; neuropathy or myopathy; and malignancy (not including squamous cell skin cancer, basal cell skin cancer, or cervical low-grade squamous intraepithelial lesions).*

*Participation may be precluded due to safety concerns or inability to adequately evaluate clinical trial endpoints.*

#### **4.3.1.3. Withdrawal from the Study or Discontinuation of the Study Product**

Participants may voluntarily withdraw their consent for study participation at any time without penalty or loss of benefits to which they are otherwise entitled.

An investigator may also withdraw a participant prior to receiving the study product or after receiving the study product for any reason. Follow-up safety evaluations will be conducted, if the participant agrees. If a

---

participant withdraws or is withdrawn prior to completion of the study, the reason for this decision must be recorded in the case report forms (CRFs).

The reasons might include, but are not limited to the following:

- Participant becomes pregnant prior to infusion.
- Participant no longer meets eligibility criteria (e.g., develops acute febrile illness on Day 1 prior to infusion).
- Participant meets individual halting criteria.
- Participant becomes non-adherent.
- Participant develops a medical disease or condition, or new clinical finding(s) for which continued participation, in the opinion of the investigator might compromise the safety of the participant, interfere with the participant's successful completion of this study, or interfere with the evaluation of responses.
- Participant is lost to follow-up.
- Determined by a physician's discretion to require additional therapy not indicated in the protocol to ensure participant's health and well-being.

If the participant consents, every attempt will be made to follow all AEs and pregnancies through resolution. The investigator should be explicit regarding study follow-up (e.g., safety follow-up) that might be carried out. The procedures that collect safety data for the purposes of research must be inclusive in the original informed consent or the investigator may seek subsequent informed consent using an IRB/IEC-approved consent form with the revised procedures.

The investigator will inform the participant that already collected data will be retained and analyzed even if the participant withdraws from this study.

#### **4.3.1.4. Participant Replacement**

Participants who withdraw, or are withdrawn from this study, or are lost to follow-up after signing the informed consent form (ICF) and receiving an infusion will not be replaced. Participants who withdraw, or are withdrawn from this study, or are lost to follow-up after signing the ICF but before infusion may be replaced.

#### **4.3.1.5. Study Termination**

If the study is prematurely terminated by the sponsor, any regulatory authority, or the investigator for any reason, the investigator will promptly inform the study participants and assure appropriate therapy or follow-up for the participants, as necessary. The investigator will provide a detailed written explanation of the termination to the IRB.

### **4.4. Treatments**

#### **4.4.1. Treatments Administered**

Participants will receive a single IV dose of either study product or placebo. Infusions will be administered over approximately 15 minutes or 30 minutes, depending upon the volume of the infusion, in the absence of infusion reactions or non-drug, infusion related safety issues; longer infusion times will be permitted. All infusions must be completed within 4 hours of compounding.

#### **4.4.2. Identity of Investigational Product(s)**

The EV68-228-N mAb is produced by expression of genetically engineered plasmids in a *Nicotiana benthamiana* based RAMP using proprietary plasmid vectors with plant viral sequences to reduce cost and improve the speed of production. The use of an engineered strain of *N. benthamiana* in which the plant specific glycosyltransferases,  $\alpha$ 1,3 fucosyltransferase and  $\beta$ 1,2 xylosyltransferase, are mutated allows the RAMP-produced mAbs to have highly homogenous mammalian N-glycans and mitigates the potential for immunogenicity caused by carryover of plant glycans. See the IB for additional information regarding product manufacturing (7).

KBio uses an internal nomenclature system for identification of investigational products; the internal KBio nomenclature for EV68-228-N is “KB13A.1.1”. This identification number will appear on the Certificate of Analysis as well as product labeling.

#### **4.4.3. Method of Assigning Participants to Dose Cohorts (Randomization)**

Enrollment/randomization will be performed through the enrollment module in the electronic data capture system, maintained by the Statistical and Data Coordinating Center (SDCC). Eligible participants in three dose escalating cohorts will be randomized in a 5:1 ratio to receive either EV68-228-N or placebo. The randomization is based on a variable blocked scheme to provide an approximately balanced allocation to the Dose Cohorts during the study.

#### **4.4.4. Selection of Doses in the Study**

Single ascending doses (3, 10, and 30 mg/kg) of EV68-228-N had been selected for this study based on the favorable safety and tolerability profile observed in the nonclinical studies (7, 8, 9, 10, 11, 12).

#### **4.4.5. Selection and Timing of Dose for Each Participant**

This trial will evaluate the PK and safety of single ascending doses (3, 10, and 30 mg/kg) of EV68-228-N administered as IV infusion on Day 1. Dosing for each cohort will begin with two sentinel participants. There will be a minimum of 2 days of observation following dosing of the sentinels before dosing of additional participants in each cohort is authorized.

#### **4.4.6. Blinding**

All investigative site personnel, study volunteers, DMID personnel will remain blinded through database lock, with the exception of an unblinded pharmacist/verifier at the research site, an unblinded SDCC biostatistician, and a DMID manager responsible for PK sample storage. The randomization scheme will be provided to the unblinded research pharmacist at the site, who will perform dose preparation, and a pharmacy verifier who will not participate in dose preparation. The pharmacy personnel at the site will not be involved in study-related assessments or have participant contact for data collection following study drug administration. The study staff participating in the administration of study product and assessment of the participants will not be aware of the administered contents of the IV infusion in the randomized arms of the study. Study drugs will be diluted in normal saline, and they will look identical to placebo in the IV infusion bag so the study staff and the participant will not be able to determine whether placebo or active drug are being administered. The label on the IV infusion bag will not have information that can identify the contents. Individual samples are barcoded, and the barcode includes information that can match the sample to the volunteer identification number, aliquot number, treatment cohort and collection time point. The SMC will receive blinded data in aggregate and presented by cohort. The SMC may review unblinded data prepared by an unblinded biostatistician in the closed session only.

#### 4.4.7. Prior and Concomitant Therapy

Medications taken before or after dosing will be reported as Prior Medications or Concomitant Medications, respectively.

Administration of any medications, therapies, or vaccines will be recorded on the appropriate data collection form. Concomitant medications recorded will include all current medications and medications taken within 28 days prior to signing the informed consent and during the study period. Medications reported in the electronic case report form (eCRF) are limited to those taken within 28 days prior to the study drug administration or taken through the study. Prescription and over-the-counter drugs will be included as well as herbals, vitamins, and supplements.

Systemic medications that might interfere with the evaluation of the investigational product should not be used unless absolutely necessary. A participant will be withdrawn for use of excluded medications.

Medications in this category include the prohibited medications per the Participant Exclusion Criteria (Section 4.3.1.2). Prohibited medications include systemic immunosuppressive drugs, immune modulators (except acetaminophen or non-steroidal anti-inflammatory drugs), oral corticosteroids, and systemic anti-neoplastic agents. Topical, inhaled, and intranasal steroids, as well as topical anti-neoplastic agents are acceptable.

#### 4.4.8. Treatment Compliance

All participants were to receive a single dose of study product administered in the clinic.

### 4.5. Safety, Immunogenicity and Pharmacokinetic Variables

The following section describes the safety and PK endpoints of the study. As this study is a Phase 1 clinical trial in healthy adult participants, there will be no assessment of drug efficacy. For a detailed SOA, refer to [Table 2](#). Refer to Section 3 for a list of primary, secondary objectives and endpoints.

#### 4.5.1. Safety Variables

Safety will be assessed through the evaluation of AEs, SAEs, vital signs, ECGs, and clinical safety laboratory data as outlined in the SOA.

Solicited AEs will be summarized by severity for each day post administration (Days 1 - 3) and as the maximum severity over all 3 days. If the AE is still ongoing after Day 3, the time point will be defined as “Ongoing after Day 3”. Additionally, solicited AEs will be analyzed using standard techniques, such as exact confidence intervals (CIs), to summarize the proportion of participants reporting each symptom.

Unsolicited AEs will be collected from the time of infusion through Day 29.

Unsolicited AEs will be coded by MedDRA for Preferred Term (PT), High Level Group Term (HLGT) and System Organ Class (SOC). SAEs, MAAEs and NOCMCs will be collected from the time of infusion through end of study. The numbers of SAEs, MAAEs, and NOCMCs will be reported by detailed listings showing the event description, MedDRA PT, HLTG and SOC, relevant dates (product administration and AEs), severity, relatedness, and outcome for each event. Non-serious unsolicited AEs will be summarized as number and percentage of participants reporting at least one event in each MedDRA PT, HLTG and SOC, cross tabulated by severity and relationship to study product. Additionally, the proportion of participants and exact 95% CIs of AEs in aggregate and by MedDRA categories will be computed.

Clinical laboratory and hematology measurements will be collected at Screening, pre-infusion on Day 1, and Days 2, 3, 8, and 29. ECG measurements will be collected at Screening, pre-infusion and 1-hour post-infusion

on Day 1, and Day 2. VS measurements will be collected at Screening, pre-infusion, post-infusion, and 1-hour post-infusion on Day 1, and Days 2, 3, 8, 15, and 29. Clinical laboratory, ECG, and VS results will be assessed at baseline and each post-dose time point collected, using the toxicity grading scales in [Table 5](#). For continuous parameters, change from baseline will also be summarized for all post-dose time points. For definitions of baseline, refer to Section [3.3.1](#).

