## 9.7. Vital Signs and Physical Examinations

Toxicity grading criteria for VS results can be found in [Table 5](#). Vital signs will be obtained on Day 1, Day 2, Day 3, Day 8, Day 15, and Day 29 of the study. Unscheduled VS measurements will be listed, but excluded from tabular and graphical summaries by time point, except when calculating the maximum severity post baseline. Refer to Section [3.3.1](#) for the definition of baseline. If VS measurements are repeated, the following rules will be used to determine which VS measurement to use for analyses if repeat measurements occur:

1. If the first replicate is normal, then it will be used for analysis.
2. If the first and second replicates are both abnormal, then the replicate with the higher severity will be used for analysis.
3. If the first replicate is abnormal, the second replicate is normal, and the third replicate was not performed, then the first replicate will be used in the analysis.
4. If the first replicate is abnormal, the second replicate is normal, and the third replicate is normal, then the second replicate will be used in the analysis.
5. If the first replicate is abnormal, the second replicate is normal, and the third replicate is abnormal, then the abnormal replicate with the higher severity will be used for analysis.

VS parameters that have grading criteria for both decreases (result lower than normal range) and increases (result higher than normal range) will be summarized separately by direction.

VS results will be summarized in tables by parameter, Dose Cohort, and time point ([Table 68](#), [Table 69](#), [Table 70](#), [Table 71](#), [Table 72](#), [Table 73](#), and [Table 74](#)).

All individual VS measurements, including height, weight, and oximetry measurements (SpO2) will be presented in [Listing 15](#).

Focused physical examinations performed on Day 1, Day 3, and Day 8. Symptom-driven physical examinations performed on Day 15, Day 29, Day 61, Day 91 and Day 121 if indicated based on review of complete medical history and any updates obtained by interview of participants since the previous visit.

Abnormal physical exam findings will be presented in [Listing 16](#).

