## **9.8. 12-Lead Standard Electrocardiogram**

Summary of 12-lead standard ECG change in overall interpretation from baseline will be shown by Dose Cohort and time point ([Table 75](#)).

A listing of ECG overall interpretations and comments will be presented in [Listing 24](#).

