### 12.4.1 Individual Laboratory Measurements and Abnormal Laboratory Values

**Table 5: Laboratory Adverse Event Grading Scale**

Protocol Assessment	Grade 1	Grade 2	Grade 3	Grade 4
Hematology				
Hemoglobin, Low (male) g/dL	12.0 - 13.0	10.0 - 11.9	8.0 - 9.9	<8.0
Hemoglobin, Low (female) g/dL	10.5 - 11.5	9.0 - 10.4	7.5 - 8.9	<7.5
WBC, Low mm 	2,500 - 2,999	1,500 - 2,499	1,000 - 1,499	<1,000
WBC, High mm 	11,600 - 15,000	15,001 - 20,000	20,001 - 25,000	>25,000
Platelets (Decrease) mm 	125,000 - 139,000	100,000 - 124,000	25,000 - 99,000	<25,000
Chemistry				
ALT	2.0 - 3.5x ULN	>3.5 - 5.0x ULN	>5.0 - 10x ULN	>10x ULN
Creatinine	1.5 - 1.7x ULN	>1.7 - 2.0x ULN	>2.0 - 2.5x ULN	>2.5x ULN or requires dialysis
Bilirubin	1.5 - 2.0x ULN	>2.0 - 3.0x ULN	>3.0 - 5.0x ULN	>5.0x ULN
Vital Signs				
Hypertension (systolic) mmHg	141 - 150	151 - 155	>155	ER visit or hospitalization for management
Hypertension (diastolic) mmHg	91 - 95	96 - 100	>100	ER visit or hospitalization for management
Hypotension (systolic) mmHg	85-89	80-84	<80	ER visit or hospitalization for management
Bradycardia, baseline >60 bpm	50 - 54	45-49	<45	ER visit or hospitalization for management
Bradycardia, baseline <60 bpm	45-50	40-44	<40	ER visit or hospitalization for management
Tachycardia bpm	101 - 115	116 - 130	>130	ER visit or hospitalization for management
Temperature °C	38.0 - 38.4	38.5 - 38.9	39.0 - 40.0	>40

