**Table 68: Vital Signs by Maximum Severity, Time Point, and Dose Cohort – Any Assessment (continued)**

Time Point	Dose Cohort	N	None		Mild/ Grade 1		Moderate/ Grade 2		Severe/ Grade 3		Life-threatening/ Grade 4	
			n	%	n	%	n	%	n	%	n	%
Day 8	3 mg/kg EV68-228-N											
	10 mg/kg EV68-228-N											
	30 mg/kg EV68-228-N											
	Placebo											
Day 15	3 mg/kg EV68-228-N											
	10 mg/kg EV68-228-N											
	30 mg/kg EV68-228-N											
	Placebo											
Day 29	3 mg/kg EV68-228-N											
	10 mg/kg EV68-228-N											
	30 mg/kg EV68-228-N											
	Placebo											
Max Severity Post Baseline	3 mg/kg EV68-228-N											
	10 mg/kg EV68-228-N											
	30 mg/kg EV68-228-N											
	Placebo											

Notes: The “Max Severity Post Baseline” rows indicate the maximum severity experienced by each participant at any time point post baseline, including unscheduled assessments. N = Number of participants in the Safety Population.

Tables with similar format:

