## 16.2.9 Individual ECG Results

### Listing 23: 16.2.9.4: Listing of Individual ECG Parameters

[Implementation Note: This listing includes all ECG assessments, scheduled and unscheduled. Sort order: Dose Cohort, Participant ID, Parameter, Date of Assessment, Time of Assessment.]

Dose Cohort	Participant ID	Planned Time Point	Actual Study Day	Time of Assessment (hh:mm)	Replicate	Left Ventricular Hypertrophy	Right Bundle Branch Block	Left Bundle Branch Block	Advanced A-V Heart Block	Non-sinus Rhythm	Pathologic Q wave Abnormalities	Significant ST-T Wave Changes	Prolonged QTc Interval	Other
		Baseline				Yes/No	Yes/No	Yes/No	Yes/No	Yes/No	Yes/No	Yes/No	Yes/No	
		1 hour after infusion												
		Day 2												

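### SAP Section 4.5.1 promises change from baseline for vital signs and Table 5 grading of ECGs, but no planned table delivers the first and Table 5 cannot do the second

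*SAP*

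**What the plan says.** Section 4.5.1 makes two commitments in consecutive sentences. The first covers all three kinds of measurement: "Clinical laboratory, ECG, and VS results will be assessed at baseline and each post-dose time point collected, using the toxicity grading scales in" Table 5. The second is: "For continuous parameters, change from baseline will also be summarized for all post-dose time points".

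Section 9.7 turns this into output for vital signs: "VS results will be summarized in tables by parameter, Dose Cohort, and time point". It cites Tables 68 to 74, and the shell for all of them has columns for no grade and Grades 1 to 4. Section 9.8 does the same for the ECG: "Summary of 12-lead standard ECG change in overall interpretation from baseline will be shown by Dose Cohort and time point", in Table 75.

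The grade tables end with a row called *Max Severity Post Baseline*. The note under Table 68 says that these "rows indicate the maximum severity experienced by each participant at any time point post baseline, including unscheduled assessments". It does not refer to the grade at baseline.

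**The concern.** Blood pressure, pulse and temperature around the infusion are direct measures of how it is tolerated, and a 3, 10 and 30 mg/kg escalation should be able to show a dose-related drift in them. A grade count registers a shift only when a participant crosses a limit. The plan seems to recognise this, because it promises change from baseline. It then carries the promise through for laboratory values but not for vital signs. Section 1 describes the mock-ups as the outputs planned for the final analyses, so a summary with no shell is likely to be left out. The ECG sentence has a different problem: it names a grading scale that cannot be applied to an ECG.

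**Working it through.** **Commitments against outputs**

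| Measurement | Gradable with Table 5? | Change from baseline planned? |
|---|---|---|
| Laboratory | Yes (hematology and chemistry blocks) | Yes: Tables 52–54 and 65–67, Figures 6–11 |
| Vital signs | Partly (no low diastolic row, no SpO2 row) | No: Tables 68–74 are counts by grade |
| ECG | No row | Shift in overall interpretation only (Table 75); no numeric interval |

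Table 5, titled "Laboratory Adverse Event Grading Scale", contains hematology, chemistry and vital-sign blocks and nothing else.

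**Width of the ungraded bands, from the Table 5 limits**

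- Systolic pressure: in the row "Hypotension (systolic) mmHg", Grade 1 is 85–89. Hypertension Grade 1 is 141–150. Ungraded: 90 to 140, a width of 140 − 90 = 50 mmHg.
- Pulse, baseline above 60: bradycardia Grade 1 is 50–54 and tachycardia Grade 1 is 101–115. Ungraded: 55 to 100, a width of 45 bpm.
- Pulse, baseline below 60: bradycardia Grade 1 is 45–50. Ungraded: 51 to 100, a width of 49 bpm.
- Diastolic pressure: only high values are graded, so a fall of any size has no grade.

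**How much a grade count could miss (illustration)**

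The SAP gives no figure on this point and no SDs for vital signs. The inputs below are therefore assumptions, apart from the Table 5 limit and the 10 active participants per cohort (Section 5). Baselines were drawn from a normal distribution, kept within 90–140 mmHg and rounded. An independent normal fall was then subtracted. With p the proportion ending below 90 mmHg, the chance that none of 10 is graded is (1 − p)^10.

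| Baseline mean (SD) | Mean fall | SD of change | p | None of 10 graded |
|---|---|---|---|---|
| 120 (10) | 15 | 6 | 9.3% | 38% |
| 120 (10) | 15 | 10 | 13.9% | 22% |
| 120 (10) | 20 | 6 | 18.7% | 13% |
| 120 (10) | 20 | 10 | 23.3% | 7% |
| 125 (8) | 20 | 6 | 6.2% | 53% |
| 115 (12) | 20 | 10 | 35.8% | 1% |

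The last two rows are the extremes of the scenarios run for a 20 mmHg fall.

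**What the promised summary would show**

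The 95% half-width for a mean change with n = 10 is t(0.975; 9) × SD/√10, with t = 2.262.

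- SD of change 6: 2.262 × 6/3.162 = 4.3 mmHg.
- SD of change 10: 2.262 × 10/3.162 = 7.2 mmHg.

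A mean fall of 15 to 20 mmHg would be plain in such a table.

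**Post-baseline maximum**

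A participant graded before dosing and unchanged afterwards counts in *Max Severity Post Baseline*. In a cohort of 10 that is 1/10 = 10 percentage points.

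**The case against.** The strongest reply is that little is lost. Every individual vital sign, including SpO2, is in Listing 15. A clinical reaction would also be reported as an adverse event. Table 2 requires continuous cardiopulmonary monitoring during the infusion and for up to an hour afterwards. The primary endpoints are proportions with adverse events, which these tables do not alter. The bradycardia grades already depend on baseline pulse. All of this is true and limits the point's weight. It does not supply the summary that Section 4.5.1 promises, and a listing of individual values does not show a mean shift by dose.

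A reader might infer four stronger things that the SAP does not support.

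- *A large shift would be invisible.* Take a mean fall of 25 from a baseline of 125, giving a post-dose mean of 100. With an assumed baseline SD of 8–12 and SD of change of 6–10, the combined SD runs from √(64 + 36) = 10.0 to √(144 + 100) = 15.6. The proportion at 89 or below is Φ(−10.5/10.0) = 15% to Φ(−10.5/15.6) = 25%. The chance that none of 10 is graded is 0.853^10 = 20% down to 0.749^10 = 6%. Table 73 would probably show something.
- *ECG abnormalities present before dosing are counted as post-dose.* They are not. Table 75 is a shift table with separate rows for abnormality at both times and for new abnormality.
- *Carry-over of baseline grades is widespread.* Exclusion 15 bars graded laboratory values at screening. Exclusion 14 bars abnormal vital signs at screening and on Day 1. The grade tables show a Baseline row, and laboratory values have change tables.
- *Numeric QTc change could be tabulated at once.* The SAP does not confirm that post-dose intervals are recorded. Listing 23, titled "Listing of Individual ECG Parameters", has Yes/No columns, and the QTcB limits of 450 and 460 msec apply to eligibility at screening.

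**Conclusion.** Two internal contradictions stand, and both can be checked from the SAP alone: ECG results are assigned to a scale with no ECG row, and the promised change from baseline has no output for vital signs. The consequence is loss of information in the summary tables. Systolic changes of up to 50 mmHg inside the ungraded band, and any diastolic fall, appear only in Listing 15. Mean shifts are understated rather than always hidden. The band widths come directly from Table 5, but the probabilities rest on the assumed means and SDs.

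The way the post-baseline maximum ignores the baseline grade is a smaller matter. It applies mainly to:

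- pulse, for which exclusion 14 lists no limit;
- systolic pressure of 85–89, which Table 5 grades but the limits listed under exclusion 14 do not exclude;
- Day 1 pre-dose laboratory values, which Table 2 says need not be reviewed before infusion.

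The point should be corrected before the outputs are programmed. It does not affect the primary endpoints.

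**What to change.** 1. Add to Section 9.7 summary tables in the Table 52 format (n, mean, SD, median, minimum, maximum, and change from baseline) for systolic pressure, diastolic pressure, pulse and temperature, by dose. Cover 15 minutes after the start of infusion where collected, end of infusion, 1 hour after infusion, and Days 2, 3, 8, 15 and 29. Section 3.3.1 and the repeat-measurement rules in Section 9.7 already define which value to use.
2. In Section 4.5.1, take ECG out of the Table 5 sentence and state that it is summarized by shift in overall interpretation (Table 75). Add numeric QTc change at 1 hour and Day 2 only if intervals are recorded after dosing.
3. Optionally, add a shift of baseline grade against maximum post-baseline grade for vital signs and laboratory values.
4. Reconcile the Grade 1 systolic limit in the exclusion 14 footnote with Table 5. This review takes no position on which limit is right.

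The cost is four vital-sign tables, one edited sentence and, if wanted, the shift displays. The vital-sign and laboratory items use data already collected. The downside is a slightly longer output package.
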